9.1 Analysis Populations

9.1.1 Full Analysis Set Population

The full analysis set (FAS) will consist of all treated subjects in the Agili-C™ arm and all treated subjects in the SSOC arm, for whom there is a valid overall KOOS score at baseline and at least one valid overall KOOS score post-baseline. A treated subject is defined as any subject who was randomized to any of the groups, and is not defined as a subject with major entry violation (as defined below).

In the FAS population, subjects who are treatment failures (as defined in Section 5.0) will have their 24-month KOOS score imputed as their baseline KOOS score. Thus, the treatment failure imputation will provide at least one valid overall KOOS score post-baseline and these subjects will be included in the primary analysis FAS population.

For all analyses performed on the FAS population, subjects will be analyzed according to the treatment arm to which they were randomized (regardless of the treatment actually received).

Consistent with ICH-E9, subjects with major entry violations will be excluded from FAS. Major entry violation is defined by having the potential to affect trial results and the decision of whether an entry violation is considered major will be performed by the Medical Director according to the following parameter - enrolment of subject with severe exclusion criteria, such as:

1. Bony defect depth deeper than 8mm
2. Uncontained lesion - lack of vital bone wall, at least 2mm thick, completely surrounding the lesion
3. Inability to position the implant 2mm recessed relative to the articular surface
4. Articular cartilage lesions in the tibia or the patella, ICRS grades IVa or above
5. Systemic cartilage and/or bone disorder

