## 5.10 Number of Subjects

Up to 251 subjects, who were enrolled into the Pivotal study and are continuing follow up.

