### 10.2.2 Full Analysis Set

The full analysis set (FAS) will consist of all treated subjects in the Agili-C™ arm and treated subjects in the SSOC arm, for whom there is a valid overall KOOS score at baseline and at least one valid overall KOOS score post-baseline.

Consistent with ICH-E9, subjects with major entry violations will be excluded from FAS. “Major” is defined by having the potential to affect trial results and the decision of whether an entry violation is considered major will be performed by the Medical Director.

FAS will be used for the primary analysis.

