## 10.6 Statistical Analyses

### 10.6.1 Overview

The data will be summarized in tables listing the mean, standard deviation or standard error, median, minimum, maximum, and number of subjects in a group for continuous data (e.g. age, weight) or in tables listing count and percentage for categorical data (e.g. gender, previous surgical treatment). Data will be presented by visit and treatment arm. Data listings by subject will be provided. The effects of noncompliance, dropouts, and covariates, and their interactions with treatment will be assessed to determine the impact on the general applicability of results from this study.

Primary and confirmatory secondary analyses will be conducted in the FAS. All efficacy endpoints will be tested on the FAS analysis set as well. Safety analyses will be conducted on the safety analysis set composed of all treated subjects.

Deviations from the current statistical considerations, should there be any, will be described in an amendment to the protocol and/or the statistical analysis plan (SAP). Any such deviations will be justified and described in the final report as appropriate.

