## 10.7 Efficacy

### 10.7.1 Primary Endpoint Analysis

The primary endpoint analysis is described above in section 10.5. Statistical power for testing the primary efficacy hypothesis was approximated as follows. In the FAS, the mean

A Post Approval Multicenter Open-label

Randomized Controlled Trial of Agili-C™ vs.

Surgical Standard of Care (SSOC) for the  
Treatment of Joint Surface Lesions of the Knee

CLN0021-US

Rev. 8

March 29, 2022

(SD, N) improvement was 43.0 (20.1, N=160) and 20.5 (20.9, N=79) among subjects treated with Agili-C and SSOC, respectively, or a group difference of 22.5. Since this is a 5-year study, for the purpose of sample size justification, it was assumed that the sample sizes would be 75% as large, or 120 and 59, respectively. It was further assumed that the SD would be 20% higher than the maximum of 20.1 and 20.9 or 25. Under these assumptions, statistical power based on a pooled t-test with 1-sided type 1 error rate of  $\alpha=0.025$ , is 99%. If the mean improvement at 5 years is only 80% as large as observed at Month 24 for Agili-C, i.e., 34.4, or a group difference of only 13.9, then statistical power is 93.5%. Under these assumptions, as long as the group difference in mean improvements from baseline to Month 60 is at least as large as 11.2, then power is at least 80%. Further, these computations are conservative since the statistical modelling will include information for subjects up to the point of loss-to-follow-up. Therefore, statistical power appears adequate for confirming Month 60 superiority given the results from Month 24 and reasonably conservative assumptions.

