## **10.10 Sensitivity Analyses**

As noted, the Bayesian and MMRM analyses implicitly impute missing data over time.

These implicit imputations are valid under the missing at random (MAR) assumptions. The following sensitivity analyses will be performed to evaluate the if primary results depend on this assumption.

- Worst-Case Scenario assumes all missing values among Agili-C are equal to most negative observed change score, if feasible, else equal to 0 - [baseline value] and all missing values among SSOC are equal to most positive observed change score, if feasible, else equal to 100 - [baseline value].
- If the superiority finding is lost in the Worst-Case Scenario, a tipping point analysis will be performed. In this analysis, for each value X from the worst observed control subject to the best observed control subject, and for each value Y from the worse observed Agili-C subject to the best Agili-C subject, the primary analysis will be calculated imputing all missing Control subjects as X and all Agili-C subjects as Y, producing a grid over all plausible values for the control and Agili-C subjects. This grid

includes a worst case scenario, where all control subjects are imputed with the best observed control value and all Agili-C patients imputed as the worst observed Agili-C patient. The grid also includes a best case scenario, imputing controls as the worst control patient and Agili-C patients as the best observed Agili-C patients. The tipping point curve can be observed looking in the grid for the required values of (X,Y) that result in primary analysis success.

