9.3.1 Sensitivity Analyses

As noted in the appendix, a multiple imputation procedure will be used to address missing data in the primary analysis.

Several sensitivity analyses will also be provided.

- Tipping point. For each value X from the worst observed control subject to the best observed control subject, and for each value Y from the worst observed Agili-C subject to the best Agili-C subject, the primary analysis will be calculated imputing all missing Control subjects as X and all Agili-C subjects as Y, producing a grid over all plausible values for the control and Agili-C subjects. This grid includes a worst case scenario, where all control subjects are imputed with the best observed control value and all Agili-C patients imputed as the worst observed Agili-C patient. The grid also includes a best case scenario, imputing controls as the worst control patient and Agili-C patients as the best observed Agili-C patients. The tipping point curve can be observed looking in the grid for the required values of (X,Y) that result in primary analysis success.

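### The worst-case and tipping-point analyses run on the FAS, which omits non-failure subjects lost before their first post-baseline KOOS, so they do not fully bound the effect of missing data

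*SAP*

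**What the plan says.** **Who is in the FAS.** SAP 9.1.1 admits treated subjects "for whom there is a valid overall KOOS score at baseline and at least one valid overall KOOS score post-baseline". Protocol 10.2.2 has the same condition: "at least one valid overall KOOS score post-baseline". The first post-baseline KOOS is collected at Month 6, with a window of ±12 weeks (Protocol 7.3.5); none is taken at 3 months.

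**Who gets back in.** SAP 9.1.1 keeps treatment failures: "the treatment failure imputation will provide at least one valid overall KOOS score post-baseline and these subjects will be included in the primary analysis FAS". A non-failure with no post-baseline score has no such route.

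**What the sensitivity analyses do.** Protocol 10.10 sets out to test whether the primary result depends on MAR. Its first step is "Worst-Case Scenario assumes all missing values among Agili-C are equal to most negative observed change score", with missing SSOC values set to the most positive observed change. If superiority is lost there, a tipping-point grid follows. SAP 9.3.1 has the same grid, without that trigger: "the primary analysis will be calculated imputing all missing Control subjects as X and all Agili-C subjects as Y". Neither section names an analysis set. The primary analysis is on the FAS (Protocol 10.2.2 and 10.5, SAP 9.3), and Protocol 10.6.1 adds "All efficacy endpoints will be tested on the FAS analysis set as well".

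**Numbers given.** Protocol 5.10: "Up to 251 subjects, who were enrolled into the Pivotal study". Protocol 10.7.1, for Month 24 in the FAS: "SD, N) improvement was 43.0 (20.1, N=160) and 20.5 (20.9, N=79", in the order Agili-C then SSOC.

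**The concern.** A worst-case analysis is useful because it bounds what the unseen outcomes could have done to the randomised comparison. Here the analysis set is first trimmed by a rule that depends on whether outcome data exist, and the stress test is then applied to what remains. Subjects with the least data are the ones it does not reach.

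The trial is open-label with a patient-reported endpoint, and subjects can know their arm from surgery onwards, so early withdrawal could depend on arm. The Protocol also makes the tipping-point grid conditional on losing superiority in the Worst-Case Scenario. A FAS-only worst case that just passes would mean the grid is not run at all.

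**Working it through.** **1. The plan's own figures.** Pooled t-test, one-sided 0.025, 120 and 59 subjects, SD 25 (Protocol 10.7.1). Power is 99.99% at a difference of 22.5 (stated 99%), 93.5% at 13.9 (stated 93.5%) and 80.0% at 11.2 (stated at least 80%). These reproduce and this point does not touch them. SE = 25 × √(1/120 + 1/59) = 3.98.

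**2. How many subjects.** 160 + 79 = 239, and 251 − 239 = 12 (4.8% of 251). If 251 split 2:1 as about 167/84 (assumption), the gap is 167 − 160 = 7 Agili-C and 84 − 79 = 5 SSOC. This is a ceiling. The documents do not say how many of the 12, if any, lack every post-baseline KOOS.

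**3. Month 60 worst case at the planned 75% retention.** 120 and 59 are observed; 40 and 20 FAS values are missing. Extremes are assumed 2.5 SD from the Month 24 means: Y = 43.0 − 2.5 × 20.1 = −7.25 and X = 20.5 + 2.5 × 20.9 = 72.75.

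Difference = (120 × m + k₁Y)/(120 + k₁) − (59 × 20.5 + k₂X)/(59 + k₂), where m is the observed Agili-C mean.

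| Added to FAS | m = 34.4 | shift | m = 43.0 | shift |
|---|---|---|---|---|
| none (k = 40, 20) | −9.7 | – | −3.3 | – |
| 1 + 1 | −10.4 | 0.7 | −4.0 | 0.7 |
| 4 + 3 | −11.9 | 2.2 | −5.6 | 2.3 |
| 7 + 5 | −13.4 | 3.6 | −7.2 | 3.9 |

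Superiority is already lost on the FAS alone, so the grid is run either way and only its values move. At a mild grid point (missing Agili-C at no change, missing SSOC at the SSOC mean), adding 7 + 5 lowers the difference by 1.1 (m = 34.4: 5.3 to 4.2) or 1.4 (m = 43.0: 11.75 to 10.4).

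**4. Moderate missingness.** Take 16 + 8 FAS values missing at Month 60 (10%), observed means 43.0 and 20.5, SD 25, and assumed extremes −20 and +60. The SE uses the pooled SD rebuilt with the filled values. The posterior probability is approximated by the t distribution under flat priors.

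- FAS: (144 × 43 − 16 × 20)/160 − (71 × 20.5 + 8 × 60)/79 = 36.7 − 24.5 = 12.2; SE 4.01; about 0.999, pass.
- FAS + 4 + 3: (6192 − 400)/164 − (1455.5 + 660)/82 = 35.3 − 25.8 = 9.5; SE 4.04; about 0.990, pass.
- FAS + 7 + 5: (6192 − 460)/167 − (1455.5 + 780)/84 = 34.3 − 26.6 = 7.7; SE 4.06; about 0.971, below the 0.975 threshold.

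In this scenario the conclusion turns only near the ceiling. With an observed Agili-C mean of 34.4 and only 8 + 4 missing, adding 7 + 5 also turns it (9.2, about 0.993, to 4.8, about 0.900). With a mean of 43.0 and 8 + 4 missing it does not (0.9994 after the addition).

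**5. Month 24.** If all 239 had observed values, the FAS worst case would leave 22.5 unchanged. Adding 7 + 5 at the extremes of step 3 gives (160 × 43 − 7 × 7.25)/167 − (79 × 20.5 + 5 × 72.75)/84 = 40.9 − 23.6 = 17.3. Other extremes (−10/+50 to −40/+70) give 18.5 to 16.1, with SE 2.95 to 3.35. Superiority is kept throughout.

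**The case against.** **No affected subject is shown to exist.** This stands. The gap of 12 may hold major entry violations (Protocol 10.2.2), contraindicated non-implants that Protocol 10.4 removes from efficacy analyses, or FAS subjects without a Month 24 value, since 10.7.1 does not say whether 160 and 79 are the FAS or those observed at Month 24.

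**Early loss looks small.** Protocol 10.7.4 says the FAS and PP sets differ by one Agili-C subject, and PP requires a 12-month KOOS. Few losses between Months 6 and 12 make many before Month 6 less likely. The evidence is indirect, because subjects never scored are outside both sets.

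**The study covers subjects continuing follow-up.** Protocol 5.10 does say so, which fits poorly with people who left before Month 6. But Protocol 10.2.2 defines the FAS from treated subjects, and 10.7.1 starts from the Month 24 FAS, so the randomised cohort remains the reference.

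**No analysis set is named in 10.10 or 9.3.1.** True. That the FAS applies is an inference, though a firm one, because both grids rerun the primary analysis. The silence is a reason to state the set.

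**Other checks are planned.** Protocol 10.6.1 promises to assess the effects of dropouts, but gives no method. Protocol 10.6.2 and SAP 9.9 already require dropout reasons and set sizes by arm; only FAS exclusion by reason is new.

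**A reader might infer that 12 subjects were lost and that the superiority finding is unsafe.** The documents support neither. Twelve is an upper limit with other possible causes; the Month 24 difference survives even the ceiling; and at the planned Month 60 retention the worst case fails with or without these subjects.

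**Conclusion.** The gap is real and structural. A non-failure who leaves before the first post-baseline KOOS is outside the FAS, and neither sensitivity analysis sets that subject to an extreme. The Worst-Case Scenario therefore does not bound the missing data in the randomised comparison, and a narrow FAS-only pass would cancel the Protocol's tipping-point grid.

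The size is small to modest, and nil if nobody is affected. Under assumed extremes 2.5 SD from the means, the Month 60 worst-case difference falls by about 0.7 points for 1 + 1 subjects and by at most 3.6–3.9 for 7 + 5. It could change the worst-case conclusion only at moderate FAS missingness, and in the 10% example only near the ceiling. These figures rest on reading 251 as the enrolled total, 239 as the whole FAS, a 2:1 split and the assumed extremes. Subjects with only a baseline score carry almost no information on the treatment difference under MAR, so the primary result is essentially unaffected. This is a cheap improvement, not a threat to the trial's conclusion.

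**What to change.** Keep the FAS for the primary analysis. In Protocol 10.10, state that the Worst-Case Scenario and the tipping-point grid are run on the FAS plus all randomised subjects with a baseline overall KOOS who are outside the FAS only because they have no post-baseline KOOS. Analyse them by randomised arm and fill their values by the same rules (the worst-case extremes, or X and Y in the grid).

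Leave the exclusions for major entry violations and contraindicated non-implants as they are. Restoring those subjects would mix a second population change into a missing-data check. Report by arm the number outside the FAS for each reason.

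The change belongs in the Protocol, because the Month 24 result is already reported there (10.7.1). The cost is a sentence or two, one added table and a rerun on a slightly larger data set, with no new data. The downside is that the worst-case and tipping-point results become slightly less favourable if any such subjects exist.

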9.1.2 Safety Population

The safety population will consist of all patients for whom treatment with either Agili-C™ or SSOC was performed, including patients with major entry violations.

9.1.3 Per Protocol (PP) Population

The PP analysis set is the subset of FAS including subjects with no major protocol violations and with valid observations on the primary endpoint (average overall KOOS) at 12 months, at least.

9.2 General Considerations

For continuous endpoints, the descriptive statistics include: number of non-missing observations, mean, median, standard deviation, minimum and maximum. For categorical endpoints, the count and percentage will be given.

9.3 Primary Analysis

The primary analysis will be conducted on the FAS population. Complete analysis details may be found in the Adaptive Design Report in Appendix 1.

In addition to the primary Bayesian analysis, the data will be listed and summarized with descriptive statistics by arm.

The primary analysis will be repeated on the PP population.

9.3.1 Sensitivity Analyses

As noted in the appendix, a multiple imputation procedure will be used to address missing data in the primary analysis.

Several sensitivity analyses will also be provided.

- Tipping point. For each value X from the worst observed control subject to the best observed control subject, and for each value Y from the worst observed Agili-C subject to the best Agili-C subject, the primary analysis will be calculated imputing all missing Control subjects as X and all Agili-C subjects as Y, producing a grid over all plausible values for the control and Agili-C subjects. This grid includes a worst case scenario, where all control subjects are imputed with the best observed control value and all Agili-C patients imputed as the worst observed Agili-C patient. The grid also includes a best case scenario, imputing controls as the worst control patient and Agili-C patients as the best observed Agili-C patients. The tipping point curve can be observed looking in the grid for the required values of (X,Y) that result in primary analysis success.

9.4 Confirmatory Secondary Analyses

This trial has 4 confirmatory secondary endpoints that, for the final analysis, will be tested on the FAS population hierarchically in the order presented below to preserve overall Type I Error = 0.05.

The following three pairs of confirmatory hypotheses, relating to continuous endpoints, will be tested similarly to the primary endpoint final analysis as described in the preceding section:

Confirmatory I

H_0 : Change in KOOS Pain (Agili-CTM) at 24M \leq Change in KOOS Pain (SSOC) at 24M

H_1 : Change in KOOS Pain (Agili-CTM) at 24M $>$ Change in KOOS Pain (SSOC) at 24M

Confirmatory II

H_0 : Change in KOOS QOL (Agili-CTM) at 24M \leq Change in KOOS QOL (SSOC) at 24M

H_1 : Change in KOOS QOL (Agili-CTM) at 24M $>$ Change in KOOS QOL (SSOC) at 24M

Confirmatory III

H_0 : Change in KOOS ADL (Agili-CTM) at 24M \leq Change in KOOS ADL (SSOC) at 24M

H_1 : Change in KOOS ADL (Agili-CTM) at 24M $>$ Change in KOOS ADL (SSOC) at 24M

Confirmatory IV

H_0 : Response Rate (Agili-CTM) at 24M \leq Response Rate (SSOC) at 24M

H_1 : Response Rate (Agili-CTM) at 24M $>$ Response Rate (SSOC) at 24M

For Confirmatory Endpoints I-III, testing will be performed by calculating the posterior probabilities of superiority in a manner similar to the primary endpoint. (See Adaptive Design Report in the Appendix for Details). A confirmatory secondary endpoint will be considered a success if the posterior probability exceeds 0.975. Like the primary endpoint final analysis, treatment failures will have their outcome replaced with their baseline value. And for this final analysis, all subjects will have completed follow-up. However, subjects that drop out will be multiply imputed using the longitudinal model with weakly informative priors on all parameters (see Section 9).

For Confirmatory IV, the analysis will be similar, but adjusted for the dichotomous nature of the data. Let p_0 and p_1 be the responder rates at 24 months for SSOC and Agili-C, respectively. We test the hypothesis

$$H_0: p_1 = p_0 \quad \text{vs.} \quad H_A: p_1 > p_0$$

We model the responder rate independently for each arm using non-informative priors, $p_j \sim \text{Beta}(0.5, 0.5)$ for arm j . Success corresponds to posterior probability $\text{Pr}(p_1 > p_0 | \text{Data}) > 0.975$. For this analysis, treatment failures will be imputed as non-responders. Subjects with missing data due to drop out will be handled using multiple imputation, as described in Section 9. The analyses for the Confirmatory Secondary Endpoints will be repeated on the PP population.

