		CLN0021-US Rev. 8 March 29, 2022

Therefore, the statistical model used to determine the posterior probability of superiority is the Bayesian analogue to a Mixed Model for Repeated Measures (MMRM). The priors on the fixed effects are very diffuse normal distributions. The prior on the covariance matrix was made minimally informative by setting the degrees-of-parameter to a small value (0.5) and by setting the scale parameter to a relatively large value similar in magnitude to the variances observed for KOOS Overall Score changes. The *Statistical Analysis Report, Version 1.2, September 22, 2021* includes example SAS code for this analysis.

The pivotal trial SAP, Section 9.5.2 specified that analyses of secondary endpoints will be done by “performing a repeated measures analysis using a mixed effects model with terms for treatment, visit, and treatment-by-visit interaction.” As was done for the pivotal trial, for comparison purposes, MMRM will also be applied to the primary endpoint and continuous confirmatory endpoints as well as in covariate analyses designed to evaluate whether relative effectiveness varies among relevant subgroups. To provide meaningful within-group estimates from the Bayesian analysis, the values of the baseline score included as a covariate in the model will be mean centered based on the same analysis data set that served as input (i.e., FAS or PP as appropriate). This results in a within-group estimate at the mean value of the baseline covariate, which is also consistent with how SAS Proc Mixed constructs within group estimates for MMRM.

Two classes of subjects have their 24, 36, 48 & 60 month scores imputed. First, treatment failures (defined in section 12.3) have all scores subsequent to treatment failure imputed to the be their baseline values prior to the analysis. Missing data for subjects lost-to-follow-up are either implicitly imputed using maximum likelihood methods or sampling-based methods or through the use of multiple imputation. The MMRM will utilize an unstructured covariance matrix which allows variances and covariances to vary over time.

	CLN0021-US-Investigational Plan A Post Approval Multicenter Open-label Randomized Controlled Trial of Agili-C™ vs. Surgical Standard of Care (SSOC) for the Treatment of Joint Surface Lesions of the Knee	Document Number: CLN-0000002 Document Version: 8.0 Effective Date: 08-Jun-2022 (GMT+2) Page 51 of 80 CLN0021-US Rev. 8 March 29, 2022
--	--	---

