### **10.7.2 Secondary Confirmatory Endpoint Analyses**

This trial has 6 confirmatory secondary endpoints that will be tested hierarchically in the order presented below to preserve overall Type I Error = 0.05. The following confirmatory hypotheses will be tested similarly to the primary endpoint as described in the preceding section:

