4.2 Confirmatory Secondary Efficacy Endpoints

The trial will have 4 confirmatory secondary endpoints for labeling purposes:

- Change from baseline to 24 months in KOOS Pain subscore
- Change from baseline to 24 months in KOOS QOL subscore
- Change from baseline to 24 months in KOOS ADL subscore
- Overall KOOS responder rate (defined as an increase from baseline to 24 months of ≥ 30 points on overall KOOS)

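### The only binary model given for the confirmatory responder endpoint omits baseline KOOS; adjusting for it would add roughly 0 to 6 points of power in the plan's reduced-effect scenario

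*SAP*

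**What the plan says.** SAP 9.4 handles Confirmatory IV, the 24-month responder rate, separately from the continuous endpoints: "We model the responder rate independently for each arm using non-informative priors". The prior is Beta(0.5, 0.5) in each arm, and success requires the posterior probability that the Agili-C rate exceeds the SSOC rate to be above 0.975. On failures it adds: "For this analysis, treatment failures will be imputed as non-responders". Under SAP 10.3, dropouts are imputed on the continuous change scale and then dichotomised. Response is a gain of at least 30 points on overall KOOS (SAP 4.2; protocol 10.7.3 for 60 months).

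For the continuous confirmatory endpoints I to III, SAP 9.4 says "testing will be performed by calculating the posterior probabilities of superiority in a manner similar to the primary endpoint" and refers to the Adaptive Design Report. That section does not itself mention a baseline covariate.

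The covariate appears in protocol 10.5, for the Bayesian repeated-measures model: "the values of the baseline score included as a covariate in the model will be mean centered". Protocol 10.5 also says that the primary analysis reuses the pivotal trial's models. Protocol 10.7.2 introduces all six 60-month confirmatory hypotheses, the responder rate among them, with the statement that they "will be tested similarly to the primary endpoint as described in the preceding section". It gives no model specific to a binary outcome.

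**The concern.** Response depends on change, and change is follow-up minus baseline, so a subject's chance of gaining 30 points on a 0-100 scale will usually vary with the starting score. Defining response as a change from baseline does not remove that dependence. Imputing dropouts on the continuous scale does not adjust the comparison for baseline either. A strong prognostic variable that is already collected is therefore unused in the responder comparison.

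The protocol synopsis ties labelling claims to the confirmatory endpoints met in sequence, and Confirmatory VI is one of them. No power is stated for it. The Gaussian model of protocol 10.5 cannot be applied unchanged to a yes/no outcome, so the 60-month responder test is either the unadjusted Beta comparison, carried over by inference, or not specified.

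**Working it through.** **Inputs.** Protocol 10.7.1 gives 24-month improvements of 43.0 (SD 20.1) and 20.5 (SD 20.9), planning numbers of 120 and 59, a planning SD of 25, one-sided alpha of 0.025, and a reduced-effect scenario of 34.4 vs 20.5. SAP 9.4 gives the Beta(0.5, 0.5) priors and the 0.975 threshold. SAP 8 gives a 15% failure rate per arm. The correlation between baseline and change is not in the documents; 0 to -0.5 is assumed.

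**Step 1: reproduce the plan's power.** The standard error of the difference is 25 × √(1/120 + 1/59) = 3.975. The noncentrality is 13.9/3.975 = 3.50 for the reduced effect and 11.2/3.975 = 2.82 for the smaller difference that the protocol quotes. With 177 degrees of freedom, power is 93.5% and 80.0%, as stated. At 22.5 it is 99.99% (stated 99%).

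**Step 2: responder rates, assuming normal changes.**
- Reduced effect: Φ((34.4 − 30)/25) = Φ(0.176) = 0.570; Φ((20.5 − 30)/25) = Φ(−0.38) = 0.352.
- Difference 11.2, so Agili-C mean 20.5 + 11.2 = 31.7: Φ(1.7/25) = 0.527 vs 0.352.
- Observed 24-month effect: Φ(13.0/20.1) = 0.741; Φ(−9.5/20.9) = 0.325.

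**Step 3: exact power of the Beta rule at 120/59**, enumerating both binomials: 79.1% (reduced effect), 60.2% (difference 11.2), 99.98% (observed effect). Its type I error is 2.5% to 2.6%.

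**Step 4: add baseline.** The adjusted analysis is a logistic model with treatment and baseline. Without an interaction term, the standardised Agili-C rate exceeds the SSOC rate exactly when the treatment coefficient is positive. A one-sided 0.025 Wald test of that coefficient therefore stands in for a diffuse-prior posterior above 0.975. There were 4,000 simulations per cell; the Monte Carlo standard error near 80% is √(0.8 × 0.2/4000), about 0.6 points.

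| Assumed correlation | Reduced effect: adjusted power | Gain over 79.1% | Difference 11.2: adjusted power | Gain over 60.2% |
|---|---|---|---|---|
| 0 | 78.8% | −0.3 | 60.1% | −0.1 |
| −0.2 | 79.5% | 0.4 | 61.5% | 1.3 |
| −0.3 | 80.5% | 1.4 | 62.1% | 1.9 |
| −0.4 | 82.5% | 3.4 | 64.3% | 4.1 |
| −0.5 | 84.7% | 5.6 | 67.7% | 7.5 |

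A separate simulation of the reduced-effect scenario gave 79.7%, 81.0%, 82.7% and 85.4% at −0.2 to −0.5. At the observed 24-month effect both methods are at about 100%. Adjusted type I error was 2.1% to 2.6% in simulation, so there is no sign of inflation.

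**Step 5: treatment failures.** Failures are non-responders whatever their baseline, which weakens the baseline signal. With 15% failures in each arm, and the overall means and SD held at 34.4/20.5 and 25, unadjusted power is about 84% and the gain is about 0 to 3.5 points over the same range of correlations.

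**Step 6: where the gap to the primary comes from.** The 93.5% is itself from an unadjusted t-test. Moving from that to the unadjusted responder test costs 93.5 − 79.1 = 14.4 points, all of it from dichotomising at 30. Even at a correlation of −0.5, adjustment recovers only about 6 of those points.

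**The case against.** The strongest reply is that nothing here is wrong as statistics. An unadjusted comparison of proportions is valid in a randomised trial, with neither bias nor error inflation. The quoted model governs a 24-month pivotal endpoint, and at the 24-month effect its power is already about 100%. Trial success rests on the primary alone, and Confirmatory VI is last of six, reached only if every earlier null is rejected. The gain depends on a correlation that nobody has stated and is under 1 point at −0.2. Changing a test when 24-month results by arm are already printed in the protocol of an open-label study also needs justifying. All of this stands, and it limits the point to efficiency and specification.

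A reader might also infer three stronger things that the documents do not support:
- That baseline is a covariate for every other confirmatory endpoint. SAP 9.4 does not say so; it follows only from reading protocol 10.5 together with 10.7.2.
- That the Beta model is the stated 60-month test. It is the only binary model in the documents, but its use at 60 months is an inference.
- That the shortfall from 93.5% to 79% is the price of omitting baseline. Step 6 shows otherwise.

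What the reply does not answer is that the 60-month responder model is unwritten, and that adjustment is nearly free and keeps the same threshold.

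**Conclusion.** The point holds as a modest matter of efficiency and specification. The confirmatory responder comparison, as far as the documents define it, leaves out a baseline score that is collected and that the protocol's Bayesian model for continuous outcomes uses. In the plan's reduced-effect scenario, power is about 79% and adjustment is worth about 0 to 6 points. It could reach about 7 points at a difference of 11.2. It falls to about 0 to 3.5 points with 15% failures, and there is nothing to gain if the 24-month effect persists.

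These figures assume normal change scores, the same correlation in both arms, and a correlation between 0 and −0.5. They use a Wald approximation; the full Bayesian logistic model was not fitted. A claim that the responder test is invalid, or that adjustment would bring it close to the primary's power, would go beyond what the documents support.

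**What to change.** In protocol 10.7.2 and the SAP, before the 60-month analysis, state the model for Confirmatory VI:
- a Bayesian logistic model with treatment and mean-centred baseline overall KOOS, with diffuse priors written out;
- predicted rates standardised over the FAS to give p1 and p0, with success if Pr(p1 > p0 | Data) > 0.975;
- failures kept as non-responders, and dropouts imputed on the continuous scale and then dichotomised, as now;
- the Beta(0.5, 0.5) analysis reported alongside, for comparability with the pivotal trial.

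The sponsor can estimate the pooled baseline-change correlation from the 24-month data to see where in the range the gain lies.

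The cost is a paragraph of text and a short model, with no new data or patients. The downside is a small departure from the pivotal model and a short written justification, because 24-month results by arm are already known. Protocol 11.0 also schedules annual posting of effectiveness results, so a later choice would look more data-driven.
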